**IN Control: Contraception Navigator Program for Adolescents
and Young Adults in Indiana**

NCT05691270

IRB Approval Date: April 23, 2018

Protection of Human Subjects

1. Risks to Human Subjects

a. Human Subjects Involvement, Characteristics and Design

For this portion of the research proposal (Aim 2), we will focus on conducting a pilot study of the Youth Contraception Navigator (YCN) to demonstrate feasibility and effectiveness of the intervention. Specifically, we will examine whether our intervention was successful at addressing self-efficacy and barriers (both environmental and personal) to contraception access encountered at all stages of the process. The YCN, which builds upon previous work in the field of adolescent contraception access and utilization, will be comprised of both an "outreach strategy" and a "navigator program" which were developed as part of the work in a previous Aim of this proposal. My central hypothesis is that facilitating access and utilization of contraception through the YCN intervention will result in an increased use of contraception and a decreased rate of unplanned teen pregnancy.

We will implement the outreach strategy created in Aim 1b to target adolescents within Marion County, Indiana (See Section 4.3.1). The outreach strategy will provide interested adolescents with two options to initially engage with the YCN: a) Communicate directly with navigator staff via a phone call, text, or email. Following that phone call, the adolescent would be sent a link (by email and/or text) to the *My Birth Control (Navigator Version)* decision aid b) Go directly to the website where they will be directed to complete the *My Birth Control (Navigator Version)* decision aid.

After completing *My Birth Control (Navigator Version)* the adolescent will be provided with a summary that includes the methods of contraception they have indicated interested in and a ranked listing of environmental and personal barriers the adolescent is most concerned about. At this point, they will be asked if they would like to receive additional support from a navigator staff member to answer any additional questions or help in overcoming their barriers to contraception access and use. They will be asked to provide their name and preferred manner of contact (in-person, email, phone, texting). Navigator staff will then reach out to them to inquire what assistance is needed and which services might be of assistance to the adolescent.

All adolescents who engage with the YCN (see Section 4.3.4.2) will be asked if they would like to formally enroll as a study participant after completion of the *My Birth Control (Navigator Version)* decision aid. Interested adolescents will be screened for eligibility online, which includes being an English-speaking female between the ages 15-17 who lives within Marion County (determined by zip code of primary residence) and is seeking contraception. Eligible adolescents will be asked to supply their contact information and will then be contacted to a navigator staff member in order to confirm eligibility and provide verbal assent in order to participate in the study. Adolescents who do not wish to formally enroll as study participants will still be able to utilize the services of the YCN, however additional data will not be collected.

We anticipate formally enrolling 50 adolescents in our study. Additionally, after the navigation process is complete, we will ask a sub-set of study participants to provide feedback through a Post-Pilot debriefing. We anticipate recruiting 30 participants for the debriefing but will recruit until we reach thematic saturation.

b. Study Procedures, Materials, and Potential Risks

Data will be obtained from study participants at enrollment and program completion. Study participants will receive a \$25 gift card at each data collection point. If selected to participate in the Post-Pilot debriefing interview, they will receive an additional \$40 gift card.

Demographic Data. We will collect demographic characteristics such as age, race, ethnicity, zip code, and previous contraception use at study enrollment. Data will also be collected on a voluntary de-identified basis from non-study participants after completion of the *My Birth Control (Navigator Version)* decision aid.

Effectiveness and Feasibility of the YCN Intervention. We will collect the following data from study participants:

1. Satisfaction with the Contraception Navigator Program measured via an online survey filled out upon program completion to assess satisfaction with the outreach strategy, *My Birth Control (Navigator Version)* decision aid, navigator staff, and services of the navigator program.
2. After the navigation process is complete, we will ask a sub-set of study participants to provide feedback through a Post-Pilot debriefing. Our target sample size is 30 participants chosen equally from our three racial/ethnic populations for the debriefing but will recruit until we reach thematic saturation. Feedback

will be collected via a 30-minute telephone interview. Topics to be explored will include adolescent’s reasons for seeking help to obtain contraception, how they learned about the YCN and why they ultimately contacted the program. We are also interested in views about the program’s impact on access to contraception, changes occurring as a result of participation, reflections on the outreach and navigation process, barriers encountered not addressed through the program, and overall impression of the program.

Additionally we will assess the following statistics:

 • Number of unique website visitors • Number of website visits • Number of phone or email inquiries to Navigator Staff • Completion rate of the My Birth Control (Navigator Version) decision aid (i.e., # of individuals who start compared to # of individuals who complete the decision aid) • Rate of YCN Program Interest (i.e., # of individuals who request contact from navigator staff compared to # who do not) 	
 • Contact Success Rate (i.e., # of individuals endorsing wanting additional help from navigator staff compared to the # of individuals successfully contacted by navigator staff) • Penetration Rate (i.e., # of completed My Birth Control (Navigator Version) decision aids compared to estimated eligible target population within Marion County.
--	--

Success of the YCN at addressing self-efficacy as well as our selected environmental and personal barriers.
We will collect the following data from formally enrolled study participants only:

1. Contraception self-efficacy assessed at enrollment and compared to post-program completion using the validated Contraception Self-Efficacy scale.¹⁵³ This scale measures the strength of sexually active adolescent’s conviction to obtain contraception using 15 situational questions.
2. Knowledge of contraception assessed at enrollment compared to knowledge post-program completion using the validated Contraception Knowledge Assessment.¹⁵⁴
3. Environmental and Personal Barriers addressed by the navigator program measured as the number of barriers successfully addressed divided by the number of barriers identified via the barrier assessment included in the *My Birth Control (Navigator Version)* tool.
4. Contraception method preferred from *My Birth Control (Navigator Version)* compared to contraception ultimately obtained.

There are two primary risks associated with our work:

1. Loss of confidentiality is a potential, although unlikely risk.
2. There is the potential of minimal psychological risks or discomfort associated with participating in interviews, activities and/or discussions regarding sexual activity and contraception.

2. Adequacy of Protection Against Risks

a. Informed Consent and Assent

All adolescents who contact the Youth Contraception Navigator Intervention will be asked if they would like to formally enroll as a study participant. This study has IRB Approval and a waiver of parental consent was granted. Interested adolescents ages 15-17 will be asked to provide written assent at the time of study enrollment. Adolescents who do not wish to formally enroll as study participants will still be able to utilize the services of the Youth Contraception Navigator Intervention, however additional data beyond that required to utilize the services of the program will not be collected.

During the consent process, participants will be fully informed about the purpose of the study, potential risks and benefits of participation, and that their participation is voluntary. In instances where personal identifying information must be collected in order to coordinate and plan the interviews/group sessions, provide compensation, participants will be reassured that identities will not be linked to the information they provide.

Protocols, any associated tools/instruments used for data collection, and consent/assent forms will be approved prior to collecting data.

b. Protections Against Risk

Loss of confidentiality is a potential, although unlikely risk. Data access will be limited to the PI and relevant study personnel, who will use passwords for their encrypted computer system, and be trained in confidentiality procedures offered by Indiana University. All electronic data files used for data analysis purposes will be completely de-identified and anonymous. Data collected during the course of this study in the form of video or audio files will be kept in a locked file cabinet in the PI’s office, which is also kept locked, and is located in a building with keycard access. This is also true for any handwritten notes from in-person interviews/group sessions. At the end of the study we will destroy all audio and video recordings and all hard-copy data will be shredded per Indiana University requirements. Any publications or presentation of data that may result from

this research will be completely de-identified. In instances in which participants are required to provide their name and contact information so that they can be contacted or provided with compensation, this information will be decoupled from research data and stored in a separate, password-protected database on an encrypted PC accessible only by the study PI and relevant study personnel.

We will try to minimize any potential psychological risks associated with participating in the activities/interviews/discussions for Aim 2 by informing participants that answers provided will be de-identified; that any and all data associated with this research will be treated with the highest levels of security. Additionally, participants will be informed that there are no right or wrong responses and they can choose to not answer questions. We will also identify a point of contact that is trained to help persons experiencing psychological distress should any participants require such assistance.

We feel that all these procedures will be effective to minimize potential risks to participants.

c. Vulnerable Subjects, if relevant to your study

The focus of our research is adolescent females between the ages of 15-17 who are sexually active or contemplating sexual activity, and this population can certainly be considered a vulnerable population. We have chosen this group of adolescent in particular to be the subjects of our study because they are at high risk of barriers to contraception access and thus could have a resulting unplanned pregnancy. However, we believe that the risk to participation is minimal (see 2a) and the additional protections outlined in section 2b will be in place for the participants of the study.

3. Potential Benefits of the Proposed Research to Research Participants and Others

For Aim 2, the direct benefit to participating in the Youth Contraception Navigator Intervention pilot is to receive personalized assistance with obtaining hormonal contraception as well as compensation if they decide to participate in the de-briefing interviews.

There is a significant benefit to the State of Indiana and society at large, as the results of this research has the potential to help adolescents access contraception and prevent unplanned pregnancy, the results of teen pregnancy, both for the parents (higher rates of unemployment and poverty, lower educational achievement and health outcomes) and the children (poorer educational, behavior and health outcomes and higher rates of pre-term birth) born to them—can be avoided.

All of these benefits will accrue with minimal risk to subjects.

4. Importance of the Knowledge to be Gained

We will pilot test the feasibility of a Youth Contraceptive Navigator Intervention to activate adolescents to seek help in obtaining hormonal contraception through this program. We will learn about the frequency of certain environmental and personal barriers experienced and the ability for adolescents to overcome them and ultimately access contraception with the help of the Youth Contraception Navigator Intervention. The knowledge gained through this pilot testing will help inform and improve the program before it is scaled-up to improve access to contraception for adolescents in a larger geographic area within the state.

Research has shown that improving access to contraception decreases unplanned pregnancy rates. Therefore, if the Youth Contraceptive Navigator Intervention is able to improve access and subsequent utilization of contraception for adolescents, the rate of unplanned pregnancy in the state of Indiana could ultimately be lowered in the long term. This has direct implications for adolescents themselves, but also the community in which they live and could be a model that is replicated in other states or geographic areas throughout the country.

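### Follow-up hangs on an undefined program completion, with no fixed time or dropout rule, so satisfaction and pre-post scores exist only for those who reach it and two access outcomes lack a denominator

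*Combined protocol and SAP*

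**What the plan says.** Section 1b (Study Procedures, Materials, and Potential Risks) gives the collection rule for enrolled participants: "Data will be obtained from study participants at enrollment and program completion". A $25 gift card is attached to each of these points. The expected size is in section 1a: "We anticipate formally enrolling 50 adolescents in our study".

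The individual measures in section 1b are timed as follows:

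- Satisfaction is "measured via an online survey filled out upon program completion".
- Self-efficacy: "Contraception self-efficacy assessed at enrollment and compared to post-program completion using the validated Contraception Self-Efficacy scale".
- Knowledge: "Knowledge of contraception assessed at enrollment compared to knowledge post-program completion".
- Barriers addressed is a ratio of barriers resolved to barriers identified in the decision aid. No time is given for the numerator, and the participants counted are not stated.
- The preferred method is "compared to contraception ultimately obtained", again with no time point and no rule for participants whose status is unknown.
- The debriefing is also placed late: "After the navigation process is complete, we will ask a sub-set of study participants to provide feedback".

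Section 1b also lists process statistics: website visitors and visits, inquiries, the decision-aid completion rate, the program interest rate, the contact success rate and the penetration rate. A retention or program-completion rate among enrolled participants is not on the list.

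**The concern.** The only follow-up point is an event, and the event is not defined. A participant who disengages, cannot be reached again or gives up may never arrive at it, and the plan does not say whether she would still be surveyed. Enrollment and the navigator offer are also separate questions in section 1a, and asking for a navigator is not an eligibility criterion. Some enrolled participants may therefore use no navigation, and the plan does not say whether or when they complete.

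Reaching the end of navigation plausibly goes together with overcoming barriers and obtaining a method. If so, those with follow-up data are a favourable selection of those enrolled. Section 1a says the pilot is to show effectiveness as well as feasibility, and no comparison group is described, so the pre-post changes and success figures carry that claim. Without a retention rate, a reader could not judge how selective the followed group is. Follow-up time may also differ between participants, which leaves the method finally obtained without a common time frame. Data not collected after a participant stops cannot be recovered at analysis.

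**Working it through.** **Inputs.** From the documents: N = 50 enrolled (section 1a), and two data points, the second at program completion (section 1b). The documents give no dropout rate, success rate, effect size, standard deviation, alpha or power, so the 50 cannot be reproduced. Everything below uses assumed values: dropout of 10% to 40%, 80% success among completers, two-sided alpha 0.05 and 80% power.

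**Step 1: which measures depend on completion.**

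| Measure | When collected | Who can contribute, as written |
|---|---|---|
| Satisfaction | Program completion | Those who reach it |
| Self-efficacy and knowledge, change | Enrollment and after completion | Those who reach it (baseline exists for all) |
| Barriers addressed | Denominator from the decision aid; numerator untimed | Not stated |
| Method obtained against preferred | Preferred from the decision aid; obtained untimed | Not stated |
| Process statistics | Not tied to completion | Includes people who stop or decline a navigator |

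The first two rows are completers-only by the plan's own collection rule. The next two have an open denominator.

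**Step 2: bounds on a success rate.** With m participants lost and s successes among the 50 − m completers, the completers-only rate is s/(50 − m). The rate among all enrolled lies between s/50 (none of those lost succeeded) and (s + m)/50 (all of them did).

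| Dropout | Completers | Successes at 80% | All-enrolled lower | All-enrolled upper |
|---|---|---|---|---|
| 10% | 45 | 36 | 36/50 = 72% | 41/50 = 82% |
| 20% | 40 | 32 | 32/50 = 64% | 42/50 = 84% |
| 30% | 35 | 28 | 28/50 = 56% | 43/50 = 86% |
| 40% | 30 | 24 | 24/50 = 48% | 44/50 = 88% |

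At 20% dropout the 80% figure could overstate by up to 80 − 64 = 16 points or understate by up to 84 − 80 = 4. At 40% the corresponding figures are 32 and 8. The asymmetry depends on the assumed 80%: with 60% success among completers, the ranges are 48–68% at 20% dropout and 36–76% at 40%. The completers' figure overstates only if those lost succeed less often than those who finish.

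**Step 3: the pre-post scores.** Suppose completers gain 0.5 SD and those lost gain nothing. The mean change over all enrolled is then 0.5 × 40/50 = 0.40 SD at 20% dropout and 0.5 × 30/50 = 0.30 SD at 40%. Precision falls as well. By normal approximation, the detectable paired change is (1.96 + 0.84)/√n, which is 0.40 SD at n = 50, 0.44 SD at n = 40 and 0.51 SD at n = 30.

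**The case against.** The strongest reply is that the plan follows more than completers. Enrolled participants who stop still supply demographics, previous contraception use, baseline self-efficacy and knowledge, identified barriers and preferred method. The interest rate counts people who decline a navigator, and the contact success rate is set against everyone who wanted help, reached or not. All of this stands. A reader might infer that every outcome is collected only at completion, or that those who drop out contribute nothing; the documents support neither. The process statistics, however, describe reach up to first contact. They do not show what happened to an enrolled participant afterwards.

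A reader might also infer that every success figure is a completers-only figure. For barriers addressed and method obtained the text does not say so. The participants counted are simply unspecified, which is a different defect.

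It is also fair to say that completion could mean case closure or the end of the program, in which case more participants would reach it. The document cites sections of a larger proposal (4.3.1 and 4.3.4.2) that are not included, and every enrolled participant has at least one staff contact to confirm eligibility and give assent. This weakens any claim that disengaged participants never complete. It does not supply a definition, a time or a dropout rule here.

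Finally, counting every unconfirmed participant as a failure would treat survey non-response as failure and could replace an upward bias with a downward one. That is right, and it is why the fix uses this count only as a lower bound.

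**Conclusion.** The point holds in a limited form and calls for an inexpensive improvement. Satisfaction and the pre-post changes in self-efficacy and knowledge are available only for participants who reach an undefined event. Barriers addressed and contraception obtained have no stated time point or denominator. The resulting figures are likely to be too favourable, because completion plausibly overlaps with success. Certain upward bias is a tempting conclusion, but the documents do not establish it: the bounds above include all-enrolled rates higher than the completers' rate.

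The size is unknown. The ranges of 64–84% at 20% dropout and 48–88% at 40% rest on an assumed 80% success rate among completers and on assumed dropout. They show how far a completers-only figure could be from the all-enrolled rate; they are not estimates for this pilot. The debriefing shares the timing problem but is a qualitative interview, not a success rate, so the bounds do not apply to it.

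**What to change.** In section 1b, define program completion and replace the event-based follow-up with one pre-specified interval after enrollment. Send the exit survey to every enrolled participant at that time, whether or not navigation is finished or was ever used, with the existing $25 card. It should cover satisfaction, self-efficacy, knowledge, method obtained and barriers addressed.

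Report method obtained and barriers addressed over all enrolled: a lower bound with unconfirmed results counted as not achieved, a best-case upper bound, and the completers-only figure alongside. Report the share who returned the exit survey, give the number contributing to each pre-post comparison, and compare baseline scores between those with and without follow-up.

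The cost is amendment wording and a scheduled survey link, with no extra participants. The cards come to at most 50 × $25 = $1,250, which the plan already implies if all 50 complete. The downside is that reported rates will be less favourable and some surveys will arrive while navigation is still under way.

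### As written, the Penetration Rate can overstate reach, because completed decision aids are not restricted to unique, eligible Marion County adolescents but the denominator is

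*Combined protocol and SAP*

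**What the plan says.** The Penetration Rate appears among the additional statistics in section 1b (Study Procedures, Materials, and Potential Risks). It is the number of completed "decision aids compared to estimated eligible target population within Marion County". No further condition is placed on the numerator, and no source or method is given for the estimated denominator.

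Other entries in the same list are worded differently. The completion rate sets the number "of individuals who start compared to # of individuals who complete the decision aid". Web traffic is given both as "Number of unique website visitors" and as total visits.

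Section 1a describes access. Outreach is aimed at adolescents in the county: "We will implement the outreach strategy created in Aim 1b to target adolescents within Marion County, Indiana". One of the two entry routes is to "Go directly to the website where they will be directed to complete the" decision aid. Those who engage "will be asked if they would like to formally enroll as a study participant after completion of the" decision aid, and then: "Interested adolescents will be screened for eligibility online, which includes being an English-speaking female between the ages 15-17 who lives within Marion County". The criteria also include seeking contraception. People who decline enrolment may still use the services. Under Demographic Data, section 1b plans voluntary, de-identified data from non-participants once they have completed the aid.

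**The concern.** A measure of population reach needs a numerator that is a subset of its denominator. Here the numerator is a count of events and the denominator a count of eligible people. Nothing in the definition excludes a completion by someone outside the age range or county, or a second completion by the same adolescent. The neighbouring metrics show that the authors separate people from events elsewhere, yet the one rate set against the county population counts events.

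Ineligible completions are plausible. The documents describe no eligibility check ahead of the aid, and the study title covers young adults and the whole state, which is wider than ages 15-17 in one county. Targeted outreach is not a restriction on access.

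The interpretation of reach is at stake. The other listed statistics are raw counts or proportions among people already in contact with the program. Section 4 says the pilot will inform the program before it is extended to a larger area, and a coverage figure with unknown inflation is a weak basis for that.

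**Working it through.** The plan gives no value for the rate, its numerator or its denominator, so there is no figure to reproduce. The check compares the definitions and then shows how sensitive the ratio is to assumed inputs.

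**Step 1: population of each part.**
- Numerator (section 1b): completed aids, with no stated condition on eligibility, residence or uniqueness.
- Denominator (section 1b): the estimated eligible population of Marion County.
- Eligibility (section 1a): English-speaking, female, 15-17, Marion County zip code, seeking contraception. It is checked after the aid, and only for those interested in enrolling.

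The numerator is therefore not contained in the denominator by definition.

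**Step 2: effect of the numerator, denominator held correct.** Let C be completed aids, N the true eligible population, i the share of completions by ineligible people, and r the share of eligible completions that are repeats. Unique eligible completers are U = C(1 - i)(1 - r). Then

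(rate as written) / (rate for unique eligible completers) = (C/N) / (U/N) = 1 / [(1 - i)(1 - r)].

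Both i and r are assumptions; the documents give neither.

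| i | r = 0 | r = 5% | r = 10% | r = 20% |
|---|---|---|---|---|
| 0 | 1.00 | 1.05 | 1.11 | 1.25 |
| 10% | 1.11 | 1.17 | 1.23 | 1.39 |
| 25% | 1.33 | 1.40 | 1.48 | 1.67 |
| 50% | 2.00 | 2.11 | 2.22 | 2.50 |

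For example, i = 25% and r = 10% give 1/(0.75 × 0.90) = 1/0.675 = 1.48. The ratio is never below 1, and equals 1 only when i = r = 0.

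**Step 3: effect of the denominator.** Suppose the estimate actually used is a broader group D, such as all females aged 15-17 in the county, of whom a share s is eligible, so that N = sD. The ratio becomes s / [(1 - i)(1 - r)]. With r = 10% (assumed):

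| s | i = 0 | i = 10% | i = 25% | i = 50% |
|---|---|---|---|---|
| 100% | 1.11 | 1.23 | 1.48 | 2.22 |
| 75% | 0.83 | 0.93 | 1.11 | 1.67 |
| 50% | 0.56 | 0.62 | 0.74 | 1.11 |
| 25% | 0.28 | 0.31 | 0.37 | 0.56 |

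At s = 50% the rate as written runs from 0.56 to 1.11 times the true rate. The numerator error acts in one direction only, but the net direction depends on how the denominator is built.

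**The case against.** The strongest reply is that the documents are silent rather than wrong. They nowhere say that ineligible or repeat completions will be counted, outreach is aimed at county adolescents, and the expected users are described as adolescents. The text also points to sections 4.3.1 and 4.3.4.2, which are not part of the document, so a check before the aid may be described there. Voluntary data from non-participants would give partial information on who completed it. The metric has no threshold and no go/no-go role, and unique visitors, inquiries and the debriefing also bear on outreach.

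Much of this stands. A reader might infer that the rate deliberately includes completions from anyone, even program staff. The documents do not support that: they fail to exclude ineligible and repeat completions, and staff use is not mentioned at all. The planned non-participant data would help, but the definition does not use them.

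What the reply does not remove is the definition itself, which sets completed aids against an eligible-only county population. If a check ahead of the aid exists elsewhere, it would deal with eligibility but not with repeats.

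**Conclusion.** The concern holds in conditional form: the Penetration Rate as written can overstate reach. With a denominator that really is the eligible population, the numerator can only leave the rate correct or raise it. The 1.00 to 2.50 range rests wholly on assumed i and r, and nothing in the documents favours one value over another.

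A reader might go further and conclude that the rate is biased upward. The documents do not support that. The inflation is zero without ineligible or repeat completions, and because the denominator's source is not stated, an over-broad estimate could cancel or reverse it.

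The consequence is limited to how a descriptive feasibility measure is read. No hypothesis test is involved, and the planned enrolment of 50 is unaffected. It is still worth correcting, because this is the only reach figure with a population denominator and the redefinition is cheap.

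**What to change.** - Define the numerator as unique completers who meet the criteria used to build the denominator: at least female, 15-17 and a Marion County zip code.
- State the source of the denominator and whether it is limited to English speakers and to those seeking contraception. Apply the same choice to the numerator.
- Take eligibility from the screening data for enrollees and from the planned voluntary, de-identified items for everyone else. Confirm that those items include age and zip code, and add one on sex.
- Remove duplicates where they can be detected, and say how.
- Report total completions separately.
- With U known unique eligible completers, K completers of unknown eligibility and denominator N, report the bounds U/N (none of the unknowns eligible) and (U + K)/N (all eligible).

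**Cost.** One metric is redefined and one voluntary item added. The item has to fit the statements in sections 1a and 2a that limit data collection from those who do not enrol, and section 2a requires instruments to be approved before use. De-duplication will be incomplete, because voluntary, de-identified records cannot be fully linked. The reported rate may be lower, or may have to be given as a range.
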